#### **4.7. Novel Coronavirus 2019 Guidance**

Guidance for conducting clinical trials during the novel coronavirus 2019 (COVID-19) pandemic is included in [Appendix 9](#).

## 5. TREATMENTS

### 5.1. Treatments Administered

In this extension study, all patients will receive the following open-label oral study treatment:

- 80 weeks of relugolix 40 mg tablet plus a capsule containing a tablet of 1.0 mg estradiol and 0.5 mg norethindrone acetate.

Each patient will be instructed to take one tablet and one capsule per day.

**Table 5-2 Description of MVT-601-3103 Study Drugs**

Name of Investigational Product	Relugolix	Estradiol / Norethindrone Acetate
Formulation Description	Round film-coated pink tablet	A Swedish orange, over-encapsulated round film-coated white tablet with back-fill material
Dosage Form	Tablet	Capsule
Unit Dose Strength	40 mg	Estradiol 1.0 mg / norethindrone acetate 0.5 mg
Route of Administration/ Duration	Oral once daily/ 80 weeks	Oral once daily/ 80 weeks

Two protocol-specified analgesics include a first-line non-steroidal anti-inflammatory drug (NSAID) and a second-line opioid or opioid/acetaminophen (or paracetamol) combination for endometriosis-related pain relief as required. The specific analgesic drugs offered may differ for different countries or regions. A list of study-specified analgesics is provided in [Appendix 1](#). For directions on prescribing rescue analgesic medications, see Section 5.7.

### 5.2. Identity of Investigational Product

Relugolix has the chemical name 1-(4-{1-[(2,6-difluorophenyl)methyl]-5-[(dimethylamino)methyl]-3-(6-methoxy-pyridazin-3-yl)-2,4-dioxo-1,2,3,4-tetrahydrothieno[2,3-d]pyrimidin-6-yl}phenyl)-3-methoxyurea.

Estradiol (1.0 mg) and norethindrone acetate (0.5 mg) is a fixed-dose combination product.

#### 5.2.1. Product Characteristics

Relugolix has no chiral centers. The compound is slightly to partially soluble in acidic solutions but essentially insoluble at neutral pH (pH 7) and above. It is partially soluble in polar organic solvents. The compound is provided as an immediate-release pink tablet using common excipients.

The fixed-dose combination tablet of estradiol 1.0 mg and norethindrone acetate 0.5 mg is encapsulated in a gelatin capsule with sufficient common back-fill material.

### **5.3. Randomization and Stratification**

This extension study is a single-arm, open-label study, and thus, patients are not randomized or stratified upon enrollment in this study.

### **5.4. Directions for Administration**

All study patients will take a study treatment of one tablet and one capsule once daily.

The study treatment should be taken in the fasted state (other than water, tea, or coffee) in the morning, at least 1 hour before breakfast. If dosing is missed in the morning for any reason, the study treatment may be taken later in the day, under fasting conditions, at least 1 hour before or 2 hours after eating a meal. The study treatment should be taken as close as possible to the same time of morning each day.

On Week 24/Baseline 1, Week 52, and Week 104 clinic visit days, study drug will be administered in the clinic rather than at home (see Schedule of Activities in Section 1.1).

### **5.5. Dose Reduction/Dose Administration**

No toxicity-related dose reductions of study drug are permitted. Patients who experience a grade 3 or greater toxicity that cannot be ameliorated by the use of adequate medical intervention should have their treatment interrupted until the toxicity improves to a grade 2 or lower severity. Patients may subsequently be re-started on study drug with the written approval of the sponsor (or designee).

### **5.6. Storage, Packaging, and Labeling**

Study drug should be stored in an appropriate, limited-access, secure location at room temperature. Follow storage conditions described on the drug labeling. Study drug should be stored protected from light. A daily temperature log of the drug storage area must be maintained every working day. Study drug must be stored under the conditions specified on the label, and remain in the original container until dispensed. Only patients enrolled in the study may receive study drug, and only authorized site staff may supply or administer study drug. Further guidance and information for final disposition of unused study drug are provided in the Investigator Site File. The investigator is responsible for study drug accountability, reconciliation, and record maintenance, including receipt, reconciliation, and final disposition records and their secure storage.

Study drug will be labeled with the study protocol number, medication or lot/batch number, contents, directions for use, storage directions, clinical study statement, and any other labeling required by regulatory bodies in the study locations and will list Myovant Sciences GmbH as the sponsor. Patients will be instructed to store study drug at room temperature out of the reach of children.

All labels for relugolix and the estradiol/norethindrone acetate combination to be distributed will meet all applicable requirements of the US Food and Drug Administration (FDA) and Annex 13 of Good Manufacturing Practices: Manufacture of investigational medicinal products (July 2010) and/or other local regulations as applicable.

---

Please see [Appendix 1](#) for a list of protocol-specified analgesics. Further details on analgesic medication are provided in the Investigator Site File.

## 5.7. Rescue Analgesic Medications

Management of endometriosis-associated pain often requires treatment with analgesics and some patients require treatment with opioid drugs. Two tiers of pain medications are specified for this trial. The study-specified pain medications for each patient will be the same as for the parent study. Only study-specific Tier 1 and Tier 2 analgesic medications (see [Appendix 1](#)) should be taken starting with the Baseline/Week 24 visit and subsequently. Analgesic medications will be taken for control of pain and not prophylactically.

If a patient develops uncontrolled endometriosis-associated pain during the study despite use of the study-specified analgesics or an intolerance to a study-specified analgesic, please contact the medical monitor.

Short-term use of non-study specified analgesics for the treatment of an intercurrent event (eg, injury or surgery) is allowed, if required. Such events should be reported as adverse events when appropriate.

Investigators must instruct the patient on the use of ibuprofen 200 mg tablets (ie, number of tablets per dose, dosing frequency, maximum number of tablets per day). For patients who may need the Tier 2 analgesic medication, a prescription should also be written for this at the time of enrollment into this study. This is to ensure that patients do not endure unnecessary pain during the conduct of the study.

Quantities of opioids prescribed should be based on the patient's expected usage until the next study visit. Prescriptions for Tier 1 and Tier 2 rescue analgesic medications should be in accordance with their full prescribing information (ie, the local product labeling) and prescriptions for opioids should not provide for any refills. Patients should be counseled on the safe use of opioids.

Patients who are not prescribed the Tier 2 medication at the time of enrollment in this study, for example, because requirement for analgesics beyond the Tier 1 medication is not expected (eg, based on pain level and/or recent analgesic requirements) should be advised to contact the investigator if pain is inadequately controlled with the Tier 1 medication alone. To avoid experiencing extended periods of uncontrolled pain, patients who require the Tier 2 medication should get a prescription from the investigator and initiate treatment with the Tier 2 medication as soon as feasible.

Use of protocol-specified rescue analgesic medications and any other analgesics taken for any type of pain, must be recorded by the patient in the eDiary.

## 5.8. Blinding

Blinding is not applicable for this open-label extension study.

## 5.9. Study Drug Accountability and Treatment Compliance

Patients should complete their eDiary each day on study and should bring all unused and used (including partially used) study drug kits to each study visit. At the Week 24/Baseline visit and

Week 104/Early Termination visit, all used, partially used, and unused study drug kits should be retained at the site. At all other visits, only fully used study drug kits should be retained at the site. New study drug should be dispensed as described in Section 1.1 (Schedule of Activities).

Study drug accountability will be conducted and results will be recorded. If a patient is persistently noncompliant with the study treatment, it may be appropriate to withdraw the patient from the study (see Section 4.5). All patients should be reinstructed about the dosing requirement during study contacts. The authorized study personnel conducting the re-education must document the process in the patient's source records.

Because of the importance to both safety and efficacy evaluation, patients who are grossly noncompliant with eDiary completion must undergo an Unscheduled visit to evaluate reasons for noncompliance and to develop a plan to improve compliance. Failure to improve compliance may result in the sponsor withdrawing the patient from further study treatment (including study analgesics) and/or discontinuation from the study (see Section 4.5 for details).

All patients should be reinstructed about the dosing requirement and eDiary compliance during study contacts. The authorized study personnel conducting the re-education must document the process in the patient's source records.

## 5.10. Prior and Concomitant Medications and Non-Drug Therapies

### 5.10.1. Prohibited Medications

Table 5-2 provides examples of prohibited drug categories; however, it is not a comprehensive list of all restricted medications. Drugs and drug classes in Table 5-2 are prohibited at any time during the study through the Follow-Up visit, except as noted in the table. Consult the medical monitor if there is any uncertainty regarding patient use of a particular drug or drug class.

**Table 5-3 Prohibited Medications**

Drug Class	Examples	Comments
Bisphosphonates	alendronate etidronate zoledronic acid	
GnRH analogues	leuprolide acetate injection, also known as leuprorelin goserelin acetate injection	
Anti-androgens	danazol	
Anticonvulsant drugs (specified)	phenobarbital carbamazepine phenytoin valproic acid primidone	Note: All other anticonvulsants are allowed
Aromatase inhibitors	anastrozole letrozole	

Drug Class	Examples	Comments
Progestins and progestin implants	dienogest norethindrone medroxyprogesterone cyproterone etonogestrel	
Estrogens	estradiol valerate conjugated estrogens ethynyl estradiol	
Hormonal contraceptives, contraceptive patches and vaginal rings	combined or progestin only NuvaRing	
Selective estrogen receptor modulators	raloxifene bazedoxifene lasofoxifene clomifene tamoxifen	
Selective progesterone receptor modulators	mifepristone ulipristal acetate	
Over-the-counter and herbal products/teas with known hormonal activity	plant-based estrogen products “natural” thyroid supplements dihydroepiandrosterone (DHEA)	
Intrauterine devices	levonorgestrel	
Bone agents	calcitonin calcitriol ipriflavone teriparatide denosumab abaloparatide odanacatib romosozumab	Calcium and Vitamin D2 and Vitamin D3 (ergocalciferol and cholecalciferol) are allowed without restriction.
Glucocorticoids	prednisolone or prednisone dexamethasone	Anticipated use of systemic glucocorticoids at an oral prednisone-equivalent dose of more than 5 mg every other day during the study.  Note: topical, inhaled, intranasal, otic, ophthalmic, intraarticular, or intralesional subcutaneous are permitted without restriction.  Short duration (< 21 days) higher-dose glucocorticoids required for acute events are permitted during the study.

Drug Class	Examples	Comments
P-glycoprotein inducers	avasimibe carbamazepine phenytoin rifampin St. John's wort tipranavir/ritonavir f	Note: For patients requiring a short course of these drugs during the study, investigator must contact the medical monitor for approval and guidance on study drug administration during this period.
Moderate and strong P-glycoprotein- inhibitors	amiodarone azithromycin a captopril b carvedilol clarithromycin a conivaptan cyclosporin c diltiazem dronedarone erythromycin a felodipine d itraconazole e ketoconazole e lopinavir/ritonavir f quercetin quinidine ranolazine ticagrelor g verapamil	Note: For patients requiring a short course of these drugs during the study, investigator must contact the medical monitor for approval and guidance on study drug administration during this period.
Analgesic drugs other than those specified for use during the study h	Acetaminophen/paracetamol (other than any included in a study-specified analgesic) aspirin > 325 mg/day NSAIDs (other than study-specified NSAIDs) gabapentin pregabalin carbamazepine metamizole cannabinoids	Note: Aspirin ≤ 325 mg per day is allowed

Drug Class	Examples	Comments
Antidepressants New treatment or changed doses of SSRI, SNRI, or TCA antidepressants	
SNRI examples: duloxetine venlafaxine desvenlafaxine
 
SSRI examples: citalopram fluoxetine paroxetine fluvoxamine
 
TCA examples: amitriptyline doxepin desipramine nortriptyline
	
SSRI, SNRI, or TCA allowed if given at the same dose as used during the 3 months prior to the Run-In Period of MVT-601-3101 or MVT-601-3102.
 
New start, dose change or discontinuation of these drugs is not allowed during the study. Changes made for safety reasons are allowed with approval of the medical monitor.

DHEA = dihydroepiandrosterone; GnRH = gonadotropin-releasing hormone; NSAID = nonsteroidal anti-inflammatory drug; SNRI = serotonin and norepinephrine reuptake inhibitor; SSRI = selective serotonin reuptake inhibitor; TCA = tricyclic antidepressant.

- Roxithromycin is allowed.
- All other angiotensin converting enzyme inhibitors are allowed.
- Tacrolimus is allowed.
- Amlodipine and nifedipine are allowed.
- Fluconazole is allowed.
- Integrase inhibitors are allowed.
- Clopidogrel is allowed.
- For situations where non-study analgesics may be allowed, see [Section 5.7](#).

### 5.10.2. Permitted Medications

All concomitant medications used during the study will be recorded in the electronic Case Report Forms (eCRFs), including the drug generic name, dose amount, route of administration, start date, and stop date.

#### 5.10.2.1. Analgesics

All analgesics will be collected in the eDiary and recorded in the eCRFs.

### 5.10.3. Prohibited Non-Drug Therapies

Surgical treatment of endometriosis is prohibited from the Week 24/Baseline visit until the patient's final study visit unless urgently needed for patient safety.

## 6. STUDY ASSESSMENTS AND PROCEDURES

The timing of each study assessment and procedure is provided in the Schedule of Activities (see Section 1.1). Study procedures are briefly described within Section 6.5. Further details of the procedures are provided in the Investigator Site File. Guidelines to address the COVID-19 pandemic are included in [Appendix 9](#).

### 6.1. Schedule of Observations and Procedures

Assessments should be completed at the designated visit/time points as described in the Schedule of Activities (see Section 1.1). The study is divided into 2 periods: Open-Label Treatment Period and Safety Follow-Up Period. Unscheduled visits may occur as needed to evaluate patients.

### 6.2. Open-Label Treatment Period (Week 24/Baseline to Week 104)

As denoted in the Schedule of Activities (see Section 1.1), certain Week 24 visit procedures of MVT-601-3101 or MVT-601-3102 will serve as the Week 24/Baseline procedures for patients who are interested in participating in this extension study, and these Week 24 procedures will be performed under the informed consent for the parent study.

Patients will be required to sign an informed consent form for the extension study and will be eligible if they meet all of the eligibility criteria.

Once eligibility is determined, all additional Week 24/Baseline visit procedures described in the Schedule of Activities (see Section 1.1) that were not performed as part of the Week 24 visit of the parent study will be completed. These include the following:

- Informed consent (unless signed previously);
- Record concomitant medications;
- Update the patient's status in the IVRS/IWRS as being in the MVT-601-3103 and receive the lot numbers for study drug allocation;
- Dispense study treatment;
- Dispense or prescribe protocol-specified analgesic drugs;
- Transition the patient within her eDiary from the parent study to MVT-601-3103
- Take study drug dose in clinic; and
- Record adverse events, if any.

The Week 24 visit date in the parent study is defined as the date that the last procedures for the Week 24 visit were completed, acknowledging that the Week 24 visit procedures may be completed on different dates. Patients will have received their last dose of study drug in the parent study on the day prior to the Week 24/Baseline visit and will receive their first dose of study drug for this extension study in the clinic after the patient is determined to be eligible for this extension study and has provided informed consent to participate. Therefore, results of testing required for eligibility must be available on or prior to the Week 24/Baseline visit. If necessary for logistical reasons (eg, delayed availability of study drug supply on site, others), and

with sponsor/designee approval, the first dose of open label study drug for MVT-601-3103 may be administered up to 10 days following the parent study Week 24/Baseline visit. If the first dose of study drug is not given during this up to 10-day interval, the parent study follow-up procedures should be followed (ie, adverse event reporting, eDiary completion, etc.).

Patients will continue recording data in their eDiary daily and taking protocol-specified analgesics as needed until Week 52. After Week 52, the eDiary will be collected on the following schedule: Week 57 to the Week 65 visit, Week 71 to the Week 78 visit, Week 85 to the Week 91 visit, and Week 98 to the Week 104 visit. Following the Week 24/Baseline visit, on-treatment study visits will occur at Weeks 28, 32, 36, 40, 44, 48, 52, 65, 78, 91, and 104. Sites will monitor diary completion using the Trial Manager web portal throughout the study.

A telephone call will be performed at Weeks 57, 71, 85 and 98. The following activities should be completed: a concomitant medication review, an evaluation of adverse events, a review of study medication compliance, and a reminder to the patient to start recording in the eDiary daily.

Accountability for study drug will be performed at each visit. Instructions for analgesic medication usage will be reinforced at each visit.

Questionnaires are administered on the electronic tablet and on paper at each visit. These procedures should occur before any other types of study procedures are performed. When both electronic tablet and paper questionnaires are required at a visit, the electronic questionnaires should be done first. The order in which the electronic tablet and paper questionnaires should be administered are as follows:

- Electronic tablet questionnaires (in the order they appear in the tablet)
- Paper questionnaires
  - PGA for function
  - EHP Work Domain [Week24/Baseline, Week 52, Week 78, and Week 104 only]

Patients will bring their eDiary, analgesic medications, and study drug to each visit. The site must document the start and stop dates of the patient's menses.

An endometrial biopsy will have been performed at the parent study Week 24 visit for all patients who participated in MVT-601-3101 (see MVT-601-3101 protocol for details). An endometrial biopsy is required at Week 52 and the Early Termination visit for all patients. This procedure is not required at the Early Termination visit in patients whose last dose of study drug was taken during Week 32 or earlier or within four weeks after completion of the Week 52 endometrial biopsy. However, the procedure may be done if it will aid in the evaluation of an ongoing adverse event. An endometrial biopsy at Week 104 is recommended for all patients who complete the open-label extension ; however, patients will have the option to opt out. Safety monitoring for this study includes physical examination, clinical laboratory tests, pregnancy tests, and adverse event collection at each visit. Clinical chemistries will be collected at each visit. A complete blood count will be collected at Week 24/Baseline, Week 28, Week 36, Week 52, Week 65, Week 78, Week 91, and Week 104. At the Week 24/Baseline visit, Week 52 visit, and Week 104 visit, additional tests include fasting (at least 8 hours, other than water) glucose, lipid profile, and hemoglobin A1c.

Electrocardiograms will be performed at the Week 24/Baseline and the Week 52 visits.

A mammogram will be performed at Week 52 or at Week 104/Early Termination for women who are or become  $\geq 40$  years old during the study (see Section 6.5.2.9).

Bone densitometry will occur at the Week 24/Baseline, Week 36, Week 52, and Week 104/Early Termination visits. Follow-up of bone densitometry findings will proceed according to the rules described in Section 6.5.2.6.

Bone densitometry and ECGs will be submitted for central reading.

Study drug compliance will be reviewed at each visit. Fasting (other than water) for at least 8 hours is required prior to blood sampling on Week 24/Baseline and Week 52/Early Termination visits and for 1 hour after administration of the study drug in the clinic. Laboratory requisitions must indicate whether or not the patient was not fasted for their chemistry and lipid testing.

Refer to the Schedule of Activities (see Section 1.1) for information about study procedures during the Open-Label Treatment Period.

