## 1.1. Schedule of Activities

**Table 1-1 Schedule of Activities for Study MVT-601-3103**

VISIT NAME (Timing is relative to MVT-601-3101/-3102)	PERIOD											SAFETY FOLLOW-UP
	Week 24/Baseline (Week 24 of Parent Study; Baseline of Extension Study)	Week 28 and Week 32	Week 36	Week 40 and Week 44	Week 48	Week 52 a	Week 65	Week 78	Week 91	Week 104 a / Early Termination	Un- scheduled b	Follow-Up c (~30 days after last dose of study drug)
Visit Window (days)	Parent Study Day 169 -10/+20	±7	±7	±7	±7	±7	±7	±7	±7	±7	-	-3 to +18
Informed Consent	X d											
Review Eligibility Criteria	X											
Concomitant Medications e	X f	X	X	X	X	X	X	X	X	X	X	X
Vital Signs (BP, HR, Temperature)	X g	X	X	X	X	X	X	X	X	X	X h	X
Weight	X g		X			X		X		X	X h	
Complete Physical Examination	X g					X i				X j	X h	
Visual Acuity k	X g											
Signs and Symptoms- Directed Physical Examination l		X	X	X	X		X	X	X		X h	X
12-Lead ECG m	X g					X				X h	X h	
Clinical Laboratory Tests n	X g,o	X	X	X	X	X n	X	X	X	X n	X h	X ee

	PERIOD											SAFETY FOLLOW-UP
VISIT NAME (Timing is relative to MVT-601-3101/-3102)	Week 24/Baseline (Week 24 of Parent Study; Baseline of Extension Study)	Week 28 and Week 32	Week 36	Week 40 and Week 44	Week 48	Week 52 a	Week 65	Week 78	Week 91	Week 104 a / Early Termination	Un-scheduled b	Follow-Up c (~30 days after last dose of study drug)
Visit Window (days)	Parent Study Day 169 -10/+20	±7	±7	±7	±7	±7	±7	±7	±7	±7	-	-3 to +18
Pharmacodynamics Sample p	X g,n					X n				X n	X h,n	
Urinalysis	X g					X				X	X h	
Pregnancy Test (Urine)	X g	X	X	X	X	X	X	X	X	X	X h	X
Daily eDiary q	X g	X	X	X	X	X	X	X	X	X		X
Site Review of eDiary Data	X g	X	X	X	X	X	X	X	X	X	X h	X
Bone Densitometry r	X g		X			X s,t				X r,s	X h	X ce
Endometrial Biopsy	X g,u					X				X t	X h	X ce
Dispense Study Treatment	X	X	X	X	X	X	X	X	X		X h	

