- aa Collect adverse events from the time that the first dose of study drug for MVT-601-3103 is administered. Adverse events with onset prior to the first dose of study drug for MVT-601-3103 should be reported as an adverse event in the parent study (MVT-601-3101 or MVT-601-3102). If events originating in the parent study are ongoing at the time of the first dose of study drug for MVT-601-3103, please see the Case Report Form Completion Guidelines for instructions for recording the follow-up status.
- bb Patients whose menses have not resumed as of the Follow-up visit for whom there is no explanation for the lack of resumption (eg, medical procedure or medications) will be contacted by telephone 3 (+0.5) months after the Follow-Up visit to determine if menses has resumed and questioned about factors that may affect resumption of menses. If a patient is lost to follow-up, three documented attempts should be made to contact the patient by telephone. If unable to contact the patient by telephone, a certified letter must be sent to the patient.
- cc A telephone call will be performed at Weeks 57, 71, 85, and 98. The following activities should be completed: a concomitant medication review, evaluation of adverse events, and a review of eDiary and study medication compliance.
- dd For patients  $\geq 40$  years old at the time of the Week 52 visit, Week 104 visit, or Early Termination visit only. See Section 6.5.2.9.
- ee See Section 6.5.2.6, Section 6.5.2.7, and Section 6.5.2.8 to determine if additional follow-up is required.

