#### **4.6. Contraception/Pregnancy Avoidance**

All patients should be counseled at every visit to adhere to the use of protocol allowed contraceptive methods. In this study, medications and devices containing hormones for contraception are excluded, and patients must agree to use non-hormonal contraception throughout the study including through 30 days following the last dose of study drug, unless any of the following apply:

- Has a sexual partner(s) who was vasectomized at least 6 months prior to the Week 24/Baseline visit;
- Had a bilateral tubal occlusion (including ligation and blockage methods such as Essure) at least 6 months prior to the Week 24/Baseline visit (patients with Essure must have prior confirmation of tubal occlusion by hysterosalpingogram) and there must be no evidence of post-Essure syndrome;

- Has a non-hormonal intrauterine device (eg, Paragard) placed in the uterus;
- Is not sexually active with men; periodic sexual relationship(s) with men requires the use of non-hormonal contraception as described below;
- Practices total abstinence from sexual intercourse, as her preferred lifestyle; periodic abstinence is not acceptable.

The only acceptable methods of contraception for those for whom one of the above methods do not apply are:

- Condom (male or female condom) with or without spermicide (cream, spray, foam, gel, suppository, or polymer film);
- Diaphragm with spermicide (condom may or may not be used);
- Cervical cap with spermicide (condom may or may not be used); or
- Vaginal sponge impregnated with spermicide used with a condom.

Patients will be provided with information on acceptable methods of contraception as part of the informed consent process and will confirm with signing of the consent form that they understand the requirements for avoidance of pregnancy during the course of the study. Patients may not donate ova during the course of the study and for 2 months following the last dose of study drug.

A patient may start hormonal contraception 4 weeks after her last study dose of study drug provided her menstrual cycle has returned.

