Urine pregnancy tests will be performed according to the Schedule of Activities ([Table 1-1](#); including just prior to receiving the first dose of study drug), and patients will receive continued guidance with respect to the avoidance of pregnancy as part of the study procedures. Patients who become pregnant during the study will be withdrawn from the study and followed for pregnancy outcome (see Section [7.8](#)).

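### The calls at Weeks 57, 71, 85 and 98 are the only scheduled contacts between visits 13 weeks apart after Week 52, and their listed content has no contraception reminder or pregnancy question

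*Protocol*

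**What the plan says.** This refers to the later protocol text in the file, the one that contains the COVID-19 guidance in Section 4.7.

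- **Visits.** Section 6.2: "on-treatment study visits will occur at Weeks 28, 32, 36, 40, 44, 48, 52, 65, 78, 91, and 104".
- **Calls.** Section 6.2: "A telephone call will be performed at Weeks 57, 71, 85 and 98".
- **Call content, Section 6.2.** "a concomitant medication review, an evaluation of adverse events, a review of study medication compliance, and a reminder to the patient to start recording" (the reminder concerns the eDiary).
- **Call content, Table 1-1 footnote on telephone contact (lettered cc).** "a concomitant medication review, evaluation of adverse events, and a review of eDiary and study medication compliance".
- **Call content, note under Figure 4-1.** The same items as the footnote.
- **Counselling, Section 4.6.** "All patients should be counseled at every visit to adhere to the use of protocol allowed contraceptive methods". The calls are not mentioned. The section also promises that "patients will receive continued guidance with respect to the avoidance of pregnancy as part of the study procedures", without naming a contact.
- **Tests.** Table 1-1 and Section 6.2 place the urine pregnancy test at each visit. None falls at a call.
- **Methods.** Section 4.6 excludes hormonal contraception. Women without an exemption are limited to condom, diaphragm, cervical cap or sponge.
- **Consequence.** Section 4.5 requires immediate withdrawal if a patient becomes pregnant.

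**The concern.** The protocol relies on methods that depend on the woman's consistent use and gives study drug daily. It treats pregnancy as a reason to stop at once. After Week 52 the clinic contacts become much sparser, and the only scheduled conversation in each interval has a fixed agenda that leaves the subject out.

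A woman who has had a contraceptive failure, or who suspects pregnancy, may therefore speak with the site in mid-interval without being asked. She may then continue dosing until the next visit test. A question on the call helps only women who can report a failure or a suspicion. At stake is earlier cessation of study drug in those women. No efficacy or safety estimate in the statistical section changes.

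**Working it through.** The plan states no figure on this point, so there is none to reproduce. The check compares the texts and then counts weeks.

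**1. Texts side by side**

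| Topic | At visits | At the four calls |
|---|---|---|
| Adverse events | yes | yes |
| Concomitant medication | yes | yes |
| Study drug compliance and eDiary | yes | yes |
| Contraception counselling | yes (Section 4.6) | not listed |
| Urine pregnancy test | yes (Table 1-1) | not applicable |
| Question on possible pregnancy | test done | not listed |

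The three places that describe the calls agree in listing no contraception or pregnancy item.

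**2. Contacts that raise contraception or pregnancy, as written**

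- Weeks 24 to 52: visits at 28, 32, 36, 40, 44, 48 and 52, so 7 contacts in 28 weeks; 28 / 7 = 4 weeks.
- Weeks 52 to 104: visits at 65, 78, 91 and 104, so 4 contacts in 52 weeks; 52 / 4 = 13 weeks.
- Table 1-1 allows ±7 days per visit, so two successive visits, and their tests, can be 13 + 2 = 15 weeks apart.

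**3. The same count if the calls covered the subject**

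- Contacts at 57, 65, 71, 78, 85, 91, 98 and 104: 8 in 52 weeks; 52 / 8 = 6.5 weeks.
- Intervals from Week 52: 5, 8, 6, 7, 7, 6, 7, 6. The sum is 52 and the longest is 8 weeks (Week 57 to Week 65).
- With visit windows and calls on schedule (no call window is stated), the longest is the Week 57 call to a Week 65 visit one week late: 8 + 1 = 9 weeks.

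**4. Time from each call to the next scheduled test**

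65 − 57 = 8, 78 − 71 = 7, 91 − 85 = 6 and 104 − 98 = 6 weeks. This is the nominal time a woman could continue dosing after a call that did not raise the subject.

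**5. Cost, as an upper bound with no dropout**

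- 800 patients × 4 calls = 3,200 calls.
- At one minute each (assumption): 3,200 / 60 ≈ 53 hours in all.
- Over about 320 sites: 3,200 / 320 = 10 calls, or 10 minutes, per site for the whole study.
- If 1% to 5% of calls lead to a urine test (assumption): 3,200 × 0.01 = 32 to 3,200 × 0.05 = 160 extra tests.

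**The case against.** The strongest reply is that nothing is wrong as written. Counselling and testing take place at every visit, and a call need not repeat every topic. Several provisions already work between visits:

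- Each call includes an adverse event evaluation.
- The promise of continuing guidance in Section 4.6 is not limited to visits.
- Patients confirm at consent that they understand the requirements.
- Sites document menses dates.
- Section 6.4 allows an Unscheduled visit at the patient's request, with a urine test.

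In addition, the later protocol text is shown only as far as the start of Section 6.5.2.6. Its Section 7.8 on pregnancy reporting, Appendix 9, the consent form and the Investigator Site File are not shown and may cover part of this.

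Most of this stands, and it limits the weight of the point. It does not remove it. A contraceptive failure is not obviously something a patient would offer as an adverse event. Menses dates are a weak signal when Section 2.1 describes induced amenorrhea as an aim of medical treatment. An Unscheduled visit needs a trigger, and a direct question would supply one.

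A reader might infer something stronger from the Amendment 2 text in the same file. For these calls it lists a contraception reminder and the need to call the investigator if pregnancy is suspected, and its Section 4.6 has a standing instruction to call. From this one could conclude that the items were dropped by mistake or that the protocol contradicts itself. The documents do not support that. Amendment 2 is superseded, and a difference from it is not an error. The reasons for the later changes are not shown. The later Section 4.6 also adds the sentence on counselling at every visit. The older wording shows only that such items fit these calls.

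**Conclusion.** The point holds as a modest, inexpensive safety improvement, to be considered. The calls are the only scheduled contacts between visits 13 weeks apart, and none of the three lists of their content covers contraception or pregnancy. Section 4.6 does not ask patients to report a suspicion.

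Using the existing calls would shorten the longest interval between contacts that raise the subject from 13 to 8 weeks nominally, or from 15 to 9 weeks with visit windows and calls on schedule.

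It would be wrong to read this as closing a detection gap. Tests stay 13 weeks apart, and an unsuspected pregnancy is still found only at a visit. The number of women concerned is below the planned 800 by an unknown amount, because of the exemptions in Section 4.6. Without a pregnancy rate in the documents, no number of pregnancies can be claimed. The conclusion also assumes that the text not shown does not already place these items on the calls.

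**What to change.** - In Section 6.2, the telephone-contact footnote to Table 1-1 and the note under Figure 4-1, add two items to the four existing calls: a reminder of the non-hormonal contraception requirements, and a direct question on contraceptive failure or possible pregnancy.
- If the answer is yes, do a urine test at an Unscheduled visit, which Section 6.4 already allows.
- In Section 4.6, tell patients to call the investigator immediately if they suspect pregnancy, unless text not shown already does so.
- Leave the visit-based test schedule unchanged.

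The cost is a few protocol sentences, a revised call script, and the call time and unscheduled tests estimated above. Each such test is an extra trip for the woman. No new scheduled visit or call is needed.
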